7	05-Sep-2016	7.0	Substantial	Updated safety information for ibrutinib and obinutuzumab Clarification of trial endpoints – time frames Clarification of inclusion criteria – phenotype of CLL suitable for monitoring Clarification of cohorts for the extension study Clarification of the sample collection instructions Updated statistical analysis section Updated information on translational studies
8	18-Aug-2017	8.0	Substantial	Clarification of patient population sizes. Amendment of eligibility criteria. Inclusion of stopping rules for patients reaching MRD negative remission. Update to the safety information for ibrutinib and obinutuzumab. Clarification of the rates of obinutuzumab infusion on re-challenge following an IRR.
9	26-Jul-2018	9.0	Substantial	Update to the safety information for ibrutinib and obinutuzumab under precautions for use. Prophylaxis for Pneumocystis Jirovecii pneumonia (PJP) has been mandated for all patients in receipt of ibrutinib. Update to instructions on infusion rates in the absence of infusion related reactions. Confidentiality section updated to reflect the General Data Protection Regulation (GDPR) which came into effect on 25 May 2018. Update to assessments to state that central review of CT scans may be requested by the TMG. Update to sample collection instructions. No longer mandating collection of peripheral blood and first pull bone marrow aspirate films. Updates to concomitant medication section.

10	18-Jul-2019	10.0	Substantial	
Addition of guidance for interpretation of HMDS MRD reports.
 
Section 11 - Update to end of trial definition. Removal of '5 year follow-up' in end of trial definition. Patients will now followed up past 'Year 5'.

11	18-Jul-2019	10.0a	Non-substantial	
CT required at progression was previously omitted from the schedule of events; this has been corrected so that the schedule of events reflects protocol requirements.
 
Version corrected on front page of protocol.

12	24-Aug-2021	11.0	Substantial	
Addition of ACE inhibitors and ARBs as prohibited concomitant medications for patients receiving ibrutinib. This change has been made as a result of an Urgent Safety Measure implemented on 20-Aug-2021 from a risk identified in the FLAIR study. In an interim analysis for FLAIR, it was identified that participants with pre-existing hypertension or cardiac co-morbidities randomised to ibrutinib + rituximab had an elevated risk of sudden unexplained death or cardiac death, which appears to be associated predominantly with ACE inhibitors. ARBs target the same pathway as ACE inhibitors so these may be considered to also be a potential risk. This was discussed with the IcICLLe Trial Management Group and, although the number of sudden or cardiac deaths noted in the FLAIR study overall was very small, it was agreed that urgent action should be taken to limit risk to trial participants receiving ibrutinib and ACE inhibitors or ARBs.
 
ACE inhibitors and ARBs have been added to Appendix 10 – Cautioned And Prohibited Medication.

13	22-Aug-2022	12.0	Substantial	
Addition of information from Other Safety Observations Section of the Ibrutinib IB regarding Cerebrovascular Accidents.
 
Addition of further information from the Precautions and Warnings Section of the Ibrutinib IB regarding Cardiac Arrhythmias and Cardiac Failure.
 
Update to the dose ibrutinib should be reduced to from 140 mg to 280 mg, if a moderate CYP3A inhibitor must be used.
 
Update to contact details for SAE reporting.
 
Update to trial personnel details.

TRIAL SYNOPSIS

Title

IcICLLe: Assessment of the Mechanism of Action of Ibrutinib (PCI-32765) in B-cell Receptor Pathway Inhibition in Chronic Lymphocytic Leukaemia (CLL).

Trial Design

IcICLLe is a feasibility study. All patients will receive continuous oral therapy with ibrutinib (420 mg once daily (OD)) from registration until disease progression. If the patient becomes confirmed minimal residual disease (MRD) negative they will also stop treatment.

The IcICLLe extension study will evaluate the efficacy of ibrutinib plus obinutuzumab in relapse/refractory CLL patients. Relapsed/refractory patients from the IcICLLe study can transfer into this follow-on study.

Objectives

The IcICLLe study (initial phase) will investigate i) the mechanism of action of ibrutinib and ii) the biological response to ibrutinib.

The IcICLLe extension study will investigate; i) the response rate of combined ibrutinib with obinutuzumab on CLL—this will include the proportion of patients who become MRD negative—and, ii) the safety of this novel combination.

Results from the IcICLLe trial will then inform the design of a randomised phase II/III trial using response as the primary outcome measure to determine whether ibrutinib in combination with obinutuzumab, shows sufficient evidence of activity in the cohorts of patients investigated in the IcICLLe trial.

IcICLLe Outcome Measures

Primary outcome measures

Proportion of patients achieving MRD-negative remission by IWCLL criteria (depletion of CLL below 0.01% in the peripheral blood and bone marrow) in a) the initial phase of the study at or before the 6 month assessment, and b) the Extension Study at or before 9 month assessment. Independent decisions will be made for each study (initial and extension).

Secondary outcome measures:

- Best disease response to treatment: Complete Remission (CR); Complete Remission with incomplete marrow recovery (Cri) or Partial Remission (PR) with leucocytosis, assessed according to the IWCLL Response Criteria (revised 2008) (Appendix 1) in a) the initial phase of the study at or before the 6 month assessment and b) the Extension Study at or before the 9 month assessment. Independent decisions will be made for each study (initial and extension).
- 1 and 2 year progression free survival for relapsed/refractory and treatment naïve patients defined as time from date of registration to date of progression (per the 2008 IWCLL criteria) or death from any cause.
- 1 and 5 year overall survival for relapsed/refractory and treatment naïve patients, defined as the time from date of registration to the date of death from any cause.
- Toxicity of ibrutinib and obinutuzumab
- CLL cell levels as a percentage of total leucocytes in the bone marrow (BM) and absolute counts in the peripheral blood (PB).
- The proportion of patients with >5%, 0.5-5%, <0.5% CLL cells in cell cycle (expressing Ki67) in the peripheral blood and bone marrow in a) the initial phase of the study at or before the 6 month assessment and b) the Extension Study at or before the 9 month assessment.
- Change in the expression levels of CD10, CD103, CD11c, CD185, CD196, CD20, CD200, CD22, CD23, CD25, CD27, CD305, CD31, CD38, CD39, CD43, CD49d, CD5, CD79b, CD81, CD95, IgD,

IgG, or IgM on CLL cells relative to baseline by more than 50% and at least 500 arbitrary units in median fluorescence intensity.

Exploratory outcome measures:

- Change in phosphoprotein expression (including Akt, Syk, MAPK, ERK and Btk) at screening in CLL cells stimulated with immunoglobulin in the presence and absence of *in vitro* ibrutinib and during/after treatment in CLL cells stimulated with immunoglobulin measured as fluorescence intensity in arbitrary units relative to unstimulated cells/control.
- Assessment of the mechanism of response and resistance to ibrutinib and obinutuzumab in patients with lack of or failure to maintain a response or disease progression compared to those patients with good responses (mutation analysis of key BCR pathway genes, gene expression profiling and epigenetic modifications)
- Response correlated with secondary prognostic markers (such as FISH, IGHV, CD38/CD49d expression)
- Change in the expression levels of BCL2, IRF4, ZAP70, CD62L, CD184, CD80, CD40, CD11a, CD54, CD154, CCR7, CD24, CD86 on CLL cells relative to baseline by more than 50% and at least 500 arbitrary units in median fluorescence intensity.
- The absolute numbers and proportions of CD4+ and CD8+ T-cell subsets with respect to expression of CD27, CD62L, CD45RA, CCR4 and CXCR3.
- Assessment of MRD levels using novel technologies including high throughput sequencing

Patient Population**IcICLLe – initial phase – ibrutinib monotherapy**

Cohort (A) – treatment naïve CLL patients

Cohort (B) i – relapsed/refractory CLL patients

IcICLLe – Extension Study – ibrutinib and obinutuzumab combination therapy

Cohort (B) ii – ibrutinib naïve relapsed/refractory CLL patients

Cohort (B) iii – patients initially enrolled on the IcICLLe trial in cohort (B)i and treated with at least 6 months of ibrutinib therapy

Sample Size:

IcICLLe

We aim to recruit 20 patients into each cohort: 40 participants in total.

IcICLLe Extension Study

Up to 20 relapsed/refractory patients originally recruited to the IcICLLe study will transition to the extension study (cohort (B) iii). At least 20 relapsed/refractory CLL patients not previously treated in the IcICLLe study (i.e., ibrutinib naïve, cohort (B) ii) will be recruited so that the total sample size in the extension study is no more than 40 patients.

Inclusion and Exclusion Criteria**Inclusion Criteria****Cohort (A): Treatment naïve (initial phase only – 20 patients)**

- Progressive Stage A, Stage B or Stage C CLL (Appendix 7)
- CLL requiring therapy by the IWCLL criteria (Appendix 1)
- ECOG performance status (PS) of 0, 1, or 2 (Appendix 6)
- Life expectancy of at least 6 months
- Age ≥ 18
- Prepared to undergo the stipulated investigations within the trial (including bone marrow examinations)
- Able to give informed consent
- Adequate hepatic function, defined as serum aspartate transaminase (AST) or alanine transaminase (ALT) $< 2.5 \times$ upper limit of normal (ULN), and total bilirubin $\leq 1.5 \times$ ULN unless due to Gilbert's syndrome
- Adequate renal function, defined as estimated creatinine clearance ≥ 30 mL/min using the Cockcroft-Gault equation

Cohorts (B)i and (B)ii: Relapsed/refractory (initial phase 20 patients, extension phase between 20-40 patients)

- B-CLL requiring therapy according to the IWCLL guidelines
 - The leukaemia cells should co-express CD19, CD5, and CD23 and each clone should have restricted to expression of either kappa or lambda immunoglobulin light chains.
 - The levels of surface immunoglobulin, CD20, and CD79b should be low. If there is atypically strong surface immunoglobulin, CD20, or CD79b expression, or other atypical features, it may not be possible to perform the MRD monitoring required to evaluate the primary endpoint.
- Refractory/relapsed CLL defined as any of the following:
 - Failure to achieve a response (CR or PR by IWCLL Criteria) to a purine analogue alone or in combination with chemotherapy, or:
 - Relapse within 6 months of responding to a purine analogue alone or in combination with chemotherapy, or:
 - Relapse at any time after fludarabine, cyclophosphamide and rituximab (FCR) or bendamustine plus rituximab or:
 - Patients with CLL with deletion of chromosome 17p who have failed at least one previous therapy.
- ECOG PS of 0, 1, or 2 (Appendix 6)
- Life expectancy of at least 6 months
- Prepared to undergo the stipulated investigations within the trial (including bone marrow examinations)
- Age ≥ 18
- Able to give informed consent
- Ability to comply with study protocol procedures
- Adequate hepatic function, defined as serum aspartate transaminase (AST) or alanine transaminase (ALT) $< 2.5 \times$ ULN, and total bilirubin $\leq 1.5 \times$ ULN unless due to Gilbert's syndrome
- Adequate renal function, defined as estimated creatinine clearance ≥ 30 mL/min using the Cockcroft-Gault equation
- Minimum platelet count of $\geq 50 \times 10^9/L$
- Absolute neutrophil count (ANC) $\geq 1.0 \times 10^9/L$ (unless due to direct marrow infiltration by CLL (to be confirmed via bone marrow biopsy)

Cohort (B)iii: Ibrutinib treated patients (extension phase only – up to 20 patients)

- Patients enrolled on IcICLLe trial as relapsed/refractory patients who have received treatment with Ibrutinib on the IcICLLe trial for at least 6 months

Exclusion Criteria**All patients**

- Unwilling to undergo the protocol assessments including the bone marrow examinations
- Active infection (at the time of registration)¹, history of chronic or recurrent infection
- Other severe, concurrent (particularly cardiac or pulmonary) diseases or mental disorders that could interfere with their ability to participate in the study
- Use of prior investigational agents within 6 weeks
- Pregnancy or lactation
- Unwilling to use appropriate contraception during and for 18 months following treatment
- Central nervous system (CNS) involvement with CLL
- Mantle cell lymphoma
- Known HIV positive
- Patients with active Hepatitis B disease
These patients should not be treated. Hepatitis B virus (HBV) screening should be performed in all patients before initiation of treatment with ibrutinib in combination with obinutuzumab. At a minimum this should include HBsAg-status and HBcAb-status. These can be complemented with other appropriate markers as per local guidelines. Patients with positive serology for Hepatitis B defined as positivity for Hepatitis B surface antigen (HBsAg) or anti Hepatitis B core antibody (anti-HBc) are excluded from the trial.
- Active secondary malignancy excluding basal cell carcinoma.
- Currently active, clinically significant hepatic impairment Child-Pugh class B or C according to the Child Pugh classification
- Persisting severe pancytopenia (neutrophils $<1.0 \times 10^9/L$) or transfusion dependent anaemia unless due to direct marrow infiltration by CLL (to be confirmed via bone marrow biopsy)
- Active haemolysis (not controlled with Prednisolone at 20mg or less)
- Patients requiring or who have received anticoagulation treatment with warfarin or vitamin K antagonists within one week of the first dose of ibrutinib
- Patients requiring concomitant use of strong CYP3A4/5 inhibitors (section 7.8.2)
- Patients with evidence or history of transformation and/or PLL
- Major surgery within 4 weeks prior to registration
- Currently active, clinically significant cardiovascular disease, such as uncontrolled arrhythmia or Class 3 or 4 congestive heart failure or a history of myocardial infarction, unstable angina, or acute coronary syndrome within 6 months prior to registration History of stroke or intracranial haemorrhage within 6 months prior to registration
- History of severe allergic or anaphylactic reactions to humanised or murine monoclonal antibodies. Known sensitivity or allergy to murine products.
- Vaccination with a live vaccine a minimum of 28 days prior to registration.
- Patients with Progressive Multifocal Leukoencephalopathy (PML).
- No known allergy to obinutuzumab or excipients

Cohort (B)i and (B)ii: Relapsed/refractory (initial phase – 20 patients, extension phase between 20-40 patients)

- Previous treatment with ibrutinib or an alternative inhibitor of B-Cell receptor pathway

Any patients currently participating in IcICLLe and wishing to consent for the IcICLLe extension study will need to meet the relevant eligibility criteria above

¹ Patients may be considered eligible if an active infection is being treated with a short course of antibiotics during the screening period. However, a patient cannot be registered and treated on the trial until the active infection has resolved and the antibiotics have stopped.

Sponsor

Cancer Research UK Clinical Trials Unit (CRCTU)
Institute of Cancer and Genomic Sciences
University of Birmingham
[name]

IcICLLe Contact Details:

IcICLLe Trial Coordinator
Haematology Team (TAP)
Postal Address: Centre for Clinical Haematology
Queen Elizabeth Hospital
[name]
[contact]
[contact]

Email: [contact]

Schedule of Events for IcICLLe**IcICLLe Treatment Schedule (initial phase) (Schedule A)**

Assessment	Screening	2 weeks prior to treatment	Day					Month					Every 6 months after 12 months	6 months after clinical complete or MRD negative remission ²	In the event of disease progression	
			1 Pre-treatment	1 (4 hr post 1 st dose)	2	8	15	1	3	6	9	12				
Demographic data, medical history, prior diagnosis/treatments	X															
Physical Examination (height, weight, BP, ECOG)	X				X			X	X	X	X	X	X	X	X	X
Constitutional symptom assessment	X							X		X					X	X
Clinical assessment of liver, spleen and lymph nodes		X			X			X	X	X	X	X	X	X	X	X
Disease response assessment								X		X					X	X
Local analysis	Haematology and biochemistry	X	X	X	X	X	X	X	X	X	X	X	X	X	X	X
	Immunology ³	X	X												X	X
CT Scan	X								X	X ⁴					X	
ECG	X							X								
Pregnancy test		X														
Ibrutinib Administration			Continuous from day 1 (until disease progression or MRD (-)ve remission²)													
Central analysis (HMDS)	Peripheral Blood	X	X	X	X	X	X	X	X	X	X	X	X	X	X	X
	Bone Marrow Aspirate	X						X		X					X	X
	Bone Marrow Trephine Biopsy	X						X		X					X	X
Concomitant medication	X		Continuous assessment until 30 days after last administration of Ibrutinib													
Adverse Events			Continuous assessment until 30 days after last administration of Ibrutinib													

² See section 7.2.3 for procedure carried out to confirm MRD negative remission, including times points of any additional blood samples and bone marrow examinations, and stopping rules

³ including serum immunoglobulin & direct antiglobulin

⁴ Only if 3 month scan abnormal

cICLLe Extension Study Treatment Schedule (Schedule B)

Assessment	Screening	2 weeks prior to treatment	Day 0		Days 1 -15				Month								Every 6 months after 12 months	6 months after clinical complete or MRD negative remission ⁵	In the event of disease progression	
			Pre-Ibrutinib treatment	4 hr post Ibrutinib treatment	1	2	8	15	1	2	3	4	5	6	9	12				
Demographic data, medical history, previous treatment	X																			
Physical Examination (height, weight, BP, ECOG, temperature)	X		X		X	X			X		X			X	X	X	X		X	X
Constitutional symptom assessment	X								X					X					X	X
Clinical assessment of liver, spleen and lymph nodes		X	X		X	X			X		X			X	X	X	X		X	X
Disease response assessment									X						X				X	X
Local analysis	Haematology and biochemistry	X	X	X	X ⁶	X ⁵	X ⁵	X ⁵	X ⁵	(X ⁵)	X ⁵	(X ⁵)	(X ⁵)	X	X	X	X		X	X
	Immunology ⁷	X		X										X					X	X
Hepatitis B screening	X																			
CT Scan	X										X			X ⁸					X	
ECG	X								X											
Pregnancy test		X																		
Ibrutinib administration			Continuous from day 0 ⁹ (until disease progression or MRD (-)ve remission ⁵)																	
Obinutuzumab administration					X	X	X	X	X ¹⁰	X ⁸	X ⁸	X ⁸	X ⁸							
Central analysis (HMDS)	Peripheral blood		X	X	X	X	X	X	X		X			X	X	X	X		X	X
	Bone marrow aspirate and trephine biopsy		X ¹¹						X ⁹						X				X	X
Concomitant medication	X		Continuous assessment until 30 days after last administration of Ibrutinib																	
Adverse Events			Continuous assessment until 30 days after last administration of Ibrutinib																	

⁵See section 7.2.3 for procedure carried out to confirm MRD negative remission, including time-points of any additional blood samples and bone marrow examinations, and stopping rules

⁶ For patients with creatinine clearance between 30 and 50 mL/min at screening, **full blood counts and biochemistry must be carried out, before, after and 24 hours after infusion, as described in section 7.1.2**

⁷ including serum immunoglobulin & direct antiglobulin (Coombs test)

⁸ If 3 month scan abnormal

⁹Ibrutinib naïve patients receive their FIRST dose on day 0 then return to clinic 24 hours later (Day 1) to receive obinutuzumab to help reduce any possible infusion related reactions

¹⁰ Obinutuzumab treatment is on day 1 of cycles 2 to 6 (i.e. at the beginning of each month) – see section 7.1 for details

¹¹ Exception: patients rolling over from IcICLLe and re-registering within 3 months of bone marrow examination on IcICLLe do NOT need to have further bone marrow examination at screening or 1 month

ABBREVIATIONS

ABPI	ASSOCIATION OF THE BRITISH PHARMACEUTICAL INDUSTRY
AE	ADVERSE EVENT
ALT	ALANINE TRANSAMINASE
ANC	ABSOLUTE NEUTROPHIL COUNT
ASCO	AMERICAN SOCIETY OF CELLULAR ONCOLOGY
AST	ASPARTATE TRANSAMINASE
BCR	B-CELL RECEPTOR
BM	BONE MARROW
BTK	BRUTON'S TYROSINE KINASE
CLL	CHRONIC LYMPHOCYTIC LEUKAEMIA
CNS	CENTRAL NERVOUS SYSTEM
CR	COMPLETE REMISSION
Cri	COMPLETE REMISSION WITH INCOMPLETE MARROW RECOVERY
CRF	CASE REPORT FORM
CR UK	CANCER RESEARCH UK
CRCTU	CANCER RESEARCH UK CLINICAL TRIALS UNIT (UNIVERSITY OF BIRMINGHAM)
CT	COMPUTERISED TOMOGRAPHY
CTCAE	COMMON TERMINOLOGY CRITERIA FOR ADVERSE EVENTS
DCF	DATA CLARIFICATION FORM
DSUR	DEVELOPMENT SAFETY UPDATE REPORT
ECG	ELECTROCARDIOGRAMS
ECOG	EASTERN COOPERATIVE ONCOLOGY GROUP
FBC	FULL BLOOD COUNT
FCR	FLUDARABINE, CYCLOPHOSPHAMIDE AND RITUXIMAB
GCP	GOOD CLINICAL PRACTICE
GDPR	GENERAL DATA PROTECTION REGULATION
GP	GENERAL PRACTITIONER
HIV	HUMAN IMMUNODEFICIENCY VIRUS
HMDS	HAEMATOLOGICAL MALIGNANCY DIAGNOSTIC SERVICE
IB	INVESTIGATOR BROCHURE
ICF	INFORMED CONSENT FORM
IMP	INVESTIGATIONAL MEDICINAL PRODUCT
IR	IONIZING RADIATION
IRR	INFUSION RELATED REACTION
ISF	INVESTIGATOR SITE FILE
IWCLL	INTERNATIONAL WORKSHOP ON CHRONIC LYMPHOCYTIC LEUKAEMIA
LDT	LYMPHOCYTE DOUBLING TIME
MCL	MANTLE CELL LYMPHOMA
MDS	MYELODYSPLASTIC SYNDROME
MHRA	MEDICINES AND HEALTHCARE PRODUCTS REGULATORY AGENCY
MRD	MINIMAL RESIDUAL DISEASE
MRI	MAGNETIC RESONANCE IMAGING
OD	ONCE DAILY
ORR	OVERALL RESPONSE RATE

OS	OVERALL SURVIVAL

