4.2 Exclusion Criteria

All patients

- Unwilling to undergo the protocol assessments including the bone marrow examinations
- Active infection (at the time of registration)¹³, history of chronic or recurrent infection
- Other severe, concurrent (particularly cardiac or pulmonary) diseases or mental disorders that could interfere with their ability to participate in the study
- Use of prior investigational agents within 6 weeks
- Pregnancy or lactation
- Unwilling to use appropriate contraception during and for 18 months following treatment
- Central nervous system (CNS) involvement with CLL
- Mantle cell lymphoma
- Known HIV positive
- Patients with active Hepatitis B disease
These patients should not be treated. Hepatitis B virus (HBV) screening should be performed in all patients before initiation of treatment with [Ibrutinib in combination with obinutuzumab]. At a minimum this should include HBsAg-status and HBcAb-status. These can be complemented with other appropriate markers as per local guidelines. Patients with positive serology for Hepatitis B defined as positivity for Hepatitis B surface antigen (HBsAg) or anti Hepatitis B core antibody (anti-HBc) are excluded from the trial
- Active secondary malignancy excluding basal cell carcinoma
- Currently active, clinically significant hepatic impairment Child-Pugh class B or C according to the Child Pugh classification
- Persisting severe pancytopenia (neutrophils $<1.0 \times 10^9/L$) or transfusion dependent anaemia unless due to direct marrow infiltration by CLL (to be confirmed via bone marrow biopsy)
- Active haemolysis (not controlled with Prednisolone at 20 mg or less)
- Patients requiring or who have received anticoagulation treatment with warfarin or vitamin K antagonists within one week of the first dose of ibrutinib
- Patients requiring concomitant use of strong CYP3A4/5 inhibitors (section 7.8.2)
- Patients with evidence or history of transformation and/or PLL
- Major surgery within 4 weeks prior to registration
- Currently active, clinically significant cardiovascular disease, such as uncontrolled arrhythmia or Class 3 or 4 congestive heart failure or a history of myocardial infarction, unstable angina, or acute coronary syndrome within 6 months prior to registration
- History of stroke or intracranial haemorrhage within 6 months prior to registration

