5.3.1 Assessments 4 weeks prior to treatment start date

These assessments are to be performed **within the four weeks** prior to registration and following consent unless conducted as part of standard clinical practice.

Complete medical history: Detailed history of CLL, baseline clinical conditions

Complete physical examination:

- Blood pressure
- Pulse
- Temperature
- Height
- Weight
- ECOG performance status

Local laboratory tests:

Haematology:

- Haemoglobin
- Lymphocyte count
- Neutrophil count
- Platelet count
- Reticulocyte count
- White blood cell count (with differential count)

Biochemistry

- Albumin
- Alkaline Phosphatase (ALP)
- ALT or AST
- Calcium (adjusted)
- Creatinine
- eGFR
- Glucose
- LDH
- Phosphate
- Potassium
- Sodium
- Total Bilirubin
- Total Protein
- Urea
- Urate

Immunology:

- Direct coombs test
- Serum immunoglobulins and electrophoresis
- β_2 microglobulin concentration

Hepatitis B screening

- Minimum: HBsAg-status and HBcAb-status. These can be complemented with other appropriate markers as per local guidelines.
- HBV DNA PCR should be performed to if HBcAb is likely due to cross reactivity with IVIg. If this is negative the patient is eligible for screening. . Following the last dose of obinutuzumab, these patients should undergo HBV DNA PCR at all study visits for two years.

CT-scan: thorax, abdomen and pelvis to assess lymph node disease¹⁴

CT scans will be performed locally at IcICLLe trial sites. Reports may be requested for central review by members of the TMG. Redacted reports (where the patient is identified only by TNO) will be requested by email.

ECG: should be performed to assess patient for signs of atrial fibrillation

Constitutional symptom assessment: Assessments of fatigue, unintentional weight loss, fevers and night sweats.

Concomitant medication: Details should be recorded from 4 weeks before start of treatment.

¹⁴ If the patient has had a CT scan within 8 weeks of the proposed treatment start date this may be used as part of the screening process in order to reduce patient exposure to ionising radiation.

If there is any doubt regarding the immunological phenotype of the patients disease please send a peripheral blood sample to HMDS for evaluation at least two weeks prior to the screening bone marrow sample

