7.9.4 Neutropenia

Cases of Grade 3 or 4 neutropenia, including febrile neutropenia, have been reported with obinutuzumab administration. Grade 3 or 4 neutropenia has predominantly been observed in patients with CLL. Patients who experience Grade 3 or 4 neutropenia should be monitored until neutrophil values return to at least Grade 2. If treatment is necessary it should be administered in accordance with local guidelines and the administration of G-CSF should be considered.

It is strongly recommended that patients with severe and long lasting (>1 week) neutropenia receive antimicrobial prophylaxis throughout the treatment period until resolution to Grade 1 or 2. Antiviral and antifungal prophylaxis should be considered. Cases of late onset neutropenia (occurring 28 days after the end of treatment) or prolonged neutropenia (lasting more than 28 days after treatment has been completed/stopped) have also been reported. Patients with renal impairment (CrCl < 50 mL/min) are more at risk of neutropenia

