7.11.2 For obinutuzumab: Discontinuation from Study Drug

Patients must discontinue study drug if they experience any of the following:

- Pregnancy
- PML

- Anaphylaxis, acute respiratory distress; prolonged or recurrent infusion reactions.
- Grade 4 IRR: Patient should be withdrawn immediately and treatment must be discontinued permanently
- Grade 3 IRR at re-challenge despite adequate premedication: Patient must be withdrawn immediately and treatment must be discontinued permanently
- Grade 3 or 4 neutropenia or thrombocytopenia as defined by the Modified IWCLL Response Criteria (revised 2008) (Appendix 2), that has not resolved to Grade ≤ 2 and requires a treatment delay to the next Cycle, Day 1 dose by 4 weeks
- Grade ≥ 2 non-haematological toxicity that does not resolve to Grade ≤ 1 /baseline and requires a treatment delay to the next Cycle, Day 1 dose by 4 weeks

Patients may also withdraw from all aspects of study participation including data collection.

Any patient who discontinues either study drug may continue ibrutinib or obinutuzumab monotherapy at the discretion of the clinician.

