8.1.3 Monitoring pregnancies for potential Serious Adverse Events

It is important to monitor the outcome of pregnancies of patients in order to provide SAE data on congenital anomalies or birth defects.

In the event that a patient or their partner becomes pregnant during the SAE reporting period please complete a Pregnancy Notification Form (providing the patient's details) and return to the trials office within 24 hours of becoming aware. If it is the patient who is pregnant provide outcome data on a follow-up Pregnancy Notification Form. Where the patient's partner is pregnant consent must first be obtained and the patient should be given a pregnancy release of information form to give to their partner. If the partner is happy to provide information on the outcome of their pregnancy they should sign the pregnancy release of information form. Once consent has been obtained provide details of the outcome of the pregnancy on a follow-up Pregnancy Notification Form. If appropriate also complete an SAE Form as detailed below.

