8.1.4 Reporting period

Details of all AEs (except those listed above) will be documented and reported from the date of commencement of protocol defined treatment until 30 days after the administration of the last treatment (refer to Treatment Schedule A and B).

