8.2.1.4 Other Malignancies

In addition to all routine AE reporting, all new malignant tumours including solid tumours, skin malignancies and haematological malignancies are to be reported for the duration of study treatment and during the specified follow-up period.

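### Schedule B ends adverse event collection 30 days after the last ibrutinib dose, in conflict with 8.1.4 and 7.7, although obinutuzumab may continue alone; separately, pregnancy notification stops at 30 days against an 18-month contraception period

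*Protocol*

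**What the plan says.** **Adverse event window.** The Protocol gives the closing date in four places.

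- Schedule B (extension study), rows for adverse events and concomitant medication: "Continuous assessment until 30 days after last administration of Ibrutinib". Schedule A, for ibrutinib monotherapy, uses the same words.
- Section 7.11.1 places the off-treatment assessment, which includes adverse events and concomitant medication, 30 days after the last ibrutinib dose. Section 7.11.2, on obinutuzumab, has no matching assessment.
- Section 8.1.4 runs reporting "until 30 days after the administration of the last treatment (refer to Treatment Schedule A and B". It names no drug and sends the reader back to the schedules.
- Section 7.7 has concomitant drugs recorded for 30 days beyond the final dose of study treatment.

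Section 7.11.2 then provides: "Any patient who discontinues either study drug may continue ibrutinib or obinutuzumab monotherapy at the discretion of the clinician".

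**Pregnancy.** Section 8.1.3 says: "In the event that a patient or their partner becomes pregnant during the SAE reporting period please complete a Pregnancy Notification Form". The only adverse event reporting period defined is the one in 8.1.4. Section 4.2 excludes patients who are "Unwilling to use appropriate contraception during and for 18 months following treatment". Section 11 sets the end of trial at 6 months after the last patient completes protocol treatment.

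**The concern.** The row in Schedule B suits a single-drug study. Schedule B adds a second investigational product, and 7.11.2 foresees patients receiving that product alone. For them the ibrutinib anchor is the earlier date, so a site working from the schedule could stop collecting events while infusions continue. Early ibrutinib cessation is foreseen elsewhere as well: Table 4 in 7.4.1 lists cardiac events that lead to discontinuation at first occurrence.

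Safety of the combination is a stated objective of the extension study, and toxicity is a secondary outcome. The extension study has at most 40 patients, so a few uncollected events would matter to the reported incidence. The obinutuzumab events of special interest in 8.2.1.3 (serious infusion-associated events, serious infection, serious neutropenia, tumour lysis syndrome) are of the kind that would arise in the uncovered time.

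On pregnancy, the Protocol treats 18 months after treatment as a period of precaution but imposes a duty to notify for only the first 30 days of it.

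**Working it through.** **Inputs.** The obinutuzumab dose occasions in 7.1.2 are Day 1 (which may be split onto Day 2), 8, 15, 29, 57, 85, 113 and 141, eight in all. The window is 30 days (Schedule B; 8.1.4). Contraception runs 18 months (4.2). The trial ends 6 months after the last patient's treatment (section 11).

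**Closing dates if obinutuzumab continues alone to Day 141.**

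- Schedule B: closing day = last ibrutinib day + 30.
- Last-treatment wording: closing day = 141 + 30 = Day 171.
- Shortfall = 171 − (last ibrutinib day + 30).

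| Last ibrutinib day | Schedule B closes | Dose occasions after closure | Days short of Day 171 |
|---|---|---|---|
| 15 | 45 | 57, 85, 113, 141 (4 of 8) | 126 |
| 29 | 59 | 85, 113, 141 (3 of 8) | 112 |
| 57 | 87 | 113, 141 (2 of 8) | 84 |
| 85 | 115 | 141 (1 of 8) | 56 |
| 111 | 141 | none | 30 |
| 141 | 171 | none | 0 |

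From Day 111 on, no infusion falls after closure, but up to 30 days of follow-up after the last infusion is lost. If ibrutinib is the drug stopped last, the ibrutinib anchor is the later date and nothing is lost.

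**Toxicity guideline (12.6.2).** The Protocol's own figures reproduce. With at most 3 toxicities in 15 and at most 6 in 36, the exact two-stage binomial gives a 90.5% chance of passing at a 10% rate (stated 90%) and a 95.4% chance of detecting a 30% rate (stated 95%). The documents give no capture rate. As an assumption only:

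- If 95% of true toxicities were captured, the effective rate is 0.30 × 0.95 = 28.5%, and detection is about 93%.
- If 80% were captured, the effective rate is 24%, and detection is about 82%.

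This is a sensitivity range and not an estimate. The objection below explains why the real effect on the count should be limited.

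**Pregnancy.** At 30.44 days per month, 18 months is about 548 days. 548 − 30 = 518 days, or about 17.0 months, in which contraception is required and no duty to notify is stated. Notification over the full 18 months would pass the end of trial by 18 − 6 = 12 months for the last-treated patient.

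**The case against.** The best defence is that 8.1.4, the section headed as the reporting period, already covers obinutuzumab. Both drugs are defined as trial treatment in 7.1, and the reference to the schedules can be read as identifying the treatment, since Schedule B has an obinutuzumab row. Section 8.2.1.1 asks for an adverse event form at each visit, and the obinutuzumab events of special interest carry no ibrutinib anchor. On the planned course, ibrutinib outlasts obinutuzumab by months. All of this stands. It makes the defect a contradiction between passages, confined to patients who stop ibrutinib first. It does not remove the contradiction, because the table that sites work from says something different and 8.1.4 sends them to it.

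Four stronger readings are tempting and are not supported.

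- *The 12.6.2 toxicity rate is biased downward because patients who stop ibrutinib for toxicity have later events missed.* The count is per patient. Someone who stopped ibrutinib for a related grade 3 or higher toxicity is already counted, and later events cannot change that. Only patients who stopped ibrutinib for other reasons could be missed.
- *The two-year hepatitis B testing shows that reporting closes too early.* The text "these patients should undergo HBV DNA PCR at all study visits for two years" sets a testing schedule for a narrow group with antibody probably due to immunoglobulin. It runs from the last obinutuzumab dose, so continued ibrutinib may cover part or all of it. It is not a reporting period.
- *Late-onset neutropenia contradicts the window.* "Cases of late onset neutropenia (occurring 28 days after the end of treatment" is background on a known risk and sets no reporting period.
- *New malignancies are cut off at 30 days.* Section 8.2.1.4 sets a separate duty, in addition to routine reporting: they "are to be reported for the duration of study treatment and during the specified follow-up period".

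The 18 months in 4.2 is likewise a contraception criterion and not a stated reporting period. The pregnancy point is therefore a mismatch between a precaution period and a notification period, not two conflicting reporting rules.

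**Conclusion.** The point holds in two parts.

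First, Schedule B and 7.11.1 contradict 8.1.4 and 7.7 on which drug fixes the end of collection. Taken literally, Schedule B leaves up to four of eight obinutuzumab dose occasions uncovered and can close as much as 126 days early when ibrutinib stops on Day 15. That example assumes that obinutuzumab then runs its full course alone, which is near the worst case. The gap shrinks with later ibrutinib cessation and is absent when ibrutinib is the last drug stopped. What is mainly at risk is the adverse event and serious adverse event incidence reported for the combination. The 12.6.2 count is touched only through patients who stopped ibrutinib for reasons other than a related grade 3 or higher toxicity, and the documents give no number for them.

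Second, pregnancy notification leaves about 17 of the 18 months of required contraception without a stated duty to report. This rests on reading 8.1.4 as the SAE reporting period that 8.1.3 refers to, since no other is defined.

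Both parts should be corrected. Neither shows that collection is closed under every reading of the Protocol.

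**What to change.** 1. In Schedule B and 8.1.4, end adverse event collection 30 days after the last dose of ibrutinib or obinutuzumab, whichever is later. Apply the same end to the concomitant-medication row of Schedule B, in line with 7.7.
2. In 7.11.1 and 7.11.2, place the off-treatment assessment on the same date.
3. In 8.1.3, state the pregnancy notification period explicitly, aligned with the 18-month contraception period in 4.2. Reconcile it with section 11, for example by saying how notifications that arrive after the end of trial are handled.

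The cost is a wording amendment and a reminder to sites. Expect a few extra adverse event, serious adverse event or pregnancy forms. Some pregnancy notifications would arrive after the current trial end date, by up to 12 months for the last-treated patient. For a patient who ends on obinutuzumab alone, the off-treatment assessment moves to a later date.
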